9.1.9 Randomization

The timing of randomization will follow shortly after baseline assessments and final confirmation of eligibility. Participants will be encouraged to initiate treatment within 28 days of randomization. If a participant is unable to initiate treatment within 28 days, he or she may initiate XR-NTX study drug at any time until week 20 and may initiate TAU at any time during the trial. Initiation of assigned treatment will be tracked.

Participants will be randomized in a 1:1 fashion to either office-based XR-NTX or TAU using a permuted block design with randomly-sized blocks. Randomization will be stratified only by site. Participants who meet DSM-5 criteria for both opioid and alcohol use disorder (16% of CTN-0055 CHOICES pilot study participants) will be included, in addition to participants with OUD, alone.

Concomitant alcohol use disorder will be considered as a potential covariate [31], [127, 128]. Participants need not be abstinent from opioids at the time of randomization.

The randomization procedure will be conducted in a centralized process through the Data and Statistics Center (DSC). Specifically, randomization schedules will be created by the study statistician for each site. The randomization schedules will be of a randomized-block nature to ensure relative equality of assignment across condition across the recruitment period and to prevent the potential for study staff guessing the next assignment, which is heightened when a fixed block-size is used. After the baseline assessment is successfully completed, a designated site study staff member will perform the randomization. Randomization for each participant is done over the internet using the Enrollment Module in Advantage eClinical.

The DSC statistician will review the randomization data on a regular basis to ensure that the scheme is being implemented according to plan. If a participant drops out of the study at any point after randomization, the randomization slot will not be re-allocated to a new participant due to the intent-to-treat nature of the study.

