11.3 HIV Risk Assessment Battery

The Risk Assessment Battery (RAB) [146] is a self-administered assessment of engagement in activities that increase the likelihood of HIV transmission. Only sexual and drug-related HIV risk behavior items will be included, in an effort to limit instrument redundancy and participant response burden. Several scores that measure drug risk, sex risk, and total risk will be computed. It will be assessed at baseline and at weeks 4, 8, 12, 16, 20, and 24 (or the end of study visit, if not week 24).

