14.3 Timeline Follow Back (TLFB)

Timeline Follow Back (TLFB) assesses self-reported drug and alcohol use over the past 30 days, with high test-retest reliability and validity [155, 156]. Participants will be asked to report daily drug and alcohol use in the specified timeframe (e.g., since the last visit). TLFB will be completed at the following visits: baseline, treatment initiation, and weeks 4, 8, 12, 16, 20, and 24 (or the end of study visit, if not week 24) for assessment of secondary outcomes. Baseline TLFB assesses use in the 30 days prior to informed consent through to the date of the baseline visit.

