17.9 Analysis of secondary outcomes

Secondary outcomes will be analyzed as indicated in the italicized text describing each secondary endpoint.

1) Secondary HIV outcomes:

- a. **Change in VACS index** at week 24 compared with randomization (score based on lab measurements). T-test.
- b. **Change in CD4 count** at 24 weeks following randomization compared with randomization (count; laboratory measurement). T-test.

2) Engagement in HIV Care:

- a. **ART prescribed** Change in the proportion of study participants prescribed ART within 24 weeks following randomization, compared to baseline (binary; medical record abstraction). *Each individual can be scored either 0 (not prescribed ART) or 1 (prescribed ART) at both baseline and follow-up, after which his or her outcome score will be the follow-up score minus the baseline score. Outcome scores will be analyzed via rank-based methods such as Wilcoxon rank-sum tests. Covariates can be considered via the cumulative logit model.*
- b. **ART Adherence** Proportion of participants taking 100% of prescribed ART doses in the past month at 24 weeks for those prescribed ART at any point during the 24 week trial (proportion; self-reported medication adherence measure). *Chi-squared test comparing proportion to treatment assignment, for those prescribed ART.*
- c. **Retention in HIV Care** Number of HIV primary care visits at 24 weeks (count, chart abstraction). *Outcome scores will be analyzed via rank-based methods such as Wilcoxon rank-sum tests.*
- d. **HIV Risk Behaviors** Past 30 day injection drug use, unprotected sex, multiple sexual partners as measured by the RAB at week 24 (binary; self-report). *Chi-squared test comparing proportion to treatment assignment.*
- e. **Quality of life** Past 30 day health-related quality of life as measured by EQ-5D at week 24. *Change from baseline in mean EQ5D score assessed by treatment group using paired t-test, or analysis of change via ordinary least squares.*

[figure not shown]
3) ART Adherence Mediation Variables and Mediation Analysis:

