- a. **Days of Opioid Use** Number of days of opioid use between baseline and 24 weeks, measured by TLFB (count; self-report), will be used to compare opioid use by treatment group. Confirmatory analysis will assess opioid use by the number of days of opioid use in the last 30 days of the study (by ASI-lite; count; self-report) and the number of monthly urine drug screen (UDS) negative for opioids between baseline and 24 weeks (count; laboratory data). *Analyzed using rank-based methods such as Wilcoxon rank-sum tests.*
- b. **Opioid Abstinence** Past 30 day opioid abstinence (by Addiction Severity Index (ASI)-lite self-report, Time-Line Follow-Back (TLFB) and urine drug screen (UDS) confirmation) in the final 30 days of the 24 week trial (binary; self-report + UDS).

Analyzed via rank-based methods such as Wilcoxon rank-sum tests. Covariates can be considered via the cumulative logit model.

Mediation Analysis

Mediation will be tested using structural equation modeling with Mplus 7.3. These models estimate the effect of the intervention on the potential mediator (path a, e.g., the effect of intervention on *substance use*) and the effect of the mediator on the outcome or next proximal intermediate outcome (path b, e.g., the effect of *substance use* on *HIV medication adherence*). Longer mediation pathways can also be tested (e.g., a^*b^*c), and therefore the entire mediational path depicted in section 1.2.1 can be assessed in this framework. There is significant mediation if the product of these two paths (a^*b) is greater than zero (or the product of more pathways in a longer mediational chain). Statistical significance will be assessed using bias-corrected bootstrap confidence intervals on the product terms [171]. This test is by far the most powerful test of mediation [172] and can test multiple mediating pathways within a single structural model. Using the tables in Fritz and MacKinnon [171], we should have over 80% power for mediation when the standardized path coefficients (a and b) are .164, which corresponds to approximately 2.7% shared variance between the outcome and predictor variable (e.g., treatment and substance for the a-path in the example given above.) We will also examine whether there are differences in strength of mediational pathways across the opioid and alcohol disorder subgroups.

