17.9.1 Additional Statistical Tests of the Secondary Outcomes

In addition to the methods described after each secondary outcome, statistical modeling will be done using generalized estimating equations (GEEs) models as employed by Liang and Zeger [174] to allow covariate adjustment in factors such as concomitant alcohol use disorder and severity of opioid and alcohol use disorder. Those secondary outcomes that are binary will be tested with a binomial distribution and logit link as implemented in SAS; whereas those secondary outcomes that involve either continuous or ordinal variables will utilize the appropriate distribution and link function. Note that the exact method of analysis will depend on the realized distribution of the particular outcome in this trial. For example, an expected count data variable may need to be modeled using a zero-inflated Poisson regression rather than a standard Poisson regression if there are too many zero observations to fit the standard Poisson. If there is over-dispersion, a

negative binomial (or zero-inflated negative binomial) regression may be appropriate. For these secondary analyses, the overall Type I error will not be controlled.

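### Days of opioid use and HIV risk behaviours: lead with the baseline- and site-adjusted analysis in Section 17.9 (free improvement, worth about 2 to 10 points of power if the baseline correlation is 0.2 to 0.5)

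*Combined protocol and SAP*

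**What the plan says.** Section 17.9 opens by making the italicized test under each endpoint its stated analysis. The three entries at issue are:

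- **3a, days of opioid use from baseline to week 24:** "Analyzed using rank-based methods such as Wilcoxon rank-sum tests". No covariate is named.
- **2d, HIV risk behaviours:** "Past 30 day injection drug use, unprotected sex, multiple sexual partners as measured by the RAB at week 24 (binary; self-report". The test is "Chi-squared test comparing proportion to treatment assignment". No covariate is named.
- **3b, opioid abstinence in the final 30 days:** a rank-based test, followed by "Covariates can be considered via the cumulative logit model".

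Section 17.9.1 adds GEE models on top of these tests, to allow "covariate adjustment in factors such as concomitant alcohol use disorder and severity of opioid and alcohol use disorder". It gives a logit link for binary outcomes and lets the exact method depend on the distribution seen. It also says that Type I error is not controlled across the secondary analyses.

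On the data available, Section 14.3 says "Baseline TLFB assesses use in the 30 days prior to informed consent through to the date of the baseline visit". Section 11.3 says of the RAB, "It will be assessed at baseline and at weeks 4, 8, 12, 16, 20, and 24". Section 14.2 has the ASI-Lite drug items collected at baseline too. Section 9.1.9 places randomization after the baseline assessments and says "Randomization will be stratified only by site".

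**The concern.** A person's earlier behaviour usually predicts the same behaviour later. An analysis that ignores it has a wider interval than the data require, and it leaves any chance imbalance between arms at baseline in the estimate. Randomization was stratified by site, so an analysis that omits site also forgoes whatever precision the stratification bought.

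The plan does use such information elsewhere. The primary model in Section 17.2 includes site and baseline alcohol use disorder. VACS Index, CD4 count, ART prescription and EQ-5D are all analysed in 17.9 as changes from baseline or randomization. Outcomes 2d, 3a and 3b are not, and no reason is given.

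Two things are at stake. One is precision on opioid use, which is also the proposed mediator of ART adherence. The other is that two analyses of each outcome are planned, the adjusted one has an open-ended covariate list, and nothing says which is to be believed if they differ.

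**Working it through.** **1. The entries side by side**

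| Outcome | Stated test (17.9) | Covariates in the entry | Baseline measure collected |
|---|---|---|---|
| 3a, opioid days over 24 weeks | rank-sum | none | TLFB opioid days (30 days before consent up to the baseline visit) |
| 2d, three RAB behaviours at week 24 | chi-squared | none | RAB |
| 3b, 30-day abstinence | rank-based | optional, cumulative logit | TLFB, ASI-Lite; urine screen at screening |

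Section 17.9.1 covers all three with additional GEE models. Site and the endpoint's own baseline measure are not among the named factors.

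**2. The plan's own figure.** The only power figure in 17.9 is for mediation: over 80% when both standardized paths are 0.164. A simulation of the bias-corrected bootstrap at N = 350 (1,000 trials, 1,000 resamples) gave 82% with a continuous predictor and 81% with a binary arm indicator, and 0.164² = 2.7%. The figure reproduces. It says nothing about the rank-sum or chi-squared tests, for which no power is stated.

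**3. Formula for the gain.** Inputs from the documents are 175 per arm and 1:1 allocation. Assumed inputs are two-sided alpha of 0.05, unadjusted power of 80%, and a baseline-to-outcome correlation ρ. Adjustment multiplies the residual variance by 1 − ρ², so

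power = Φ( (1.960 + 0.842)/√(1 − ρ²) − 1.960 ).

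- ρ = 0.2: Φ(2.802/0.980 − 1.960) = 81.6%
- ρ = 0.3: Φ(2.802/0.954 − 1.960) = 83.6%
- ρ = 0.4: Φ(2.802/0.917 − 1.960) = 86.4%
- ρ = 0.5: Φ(2.802/0.866 − 1.960) = 89.9%

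A 5-point gain needs ρ of about 0.35 and a 10-point gain about 0.50. The starting power matters. From 90%, the gain is 2.5 points at ρ = 0.3 and 6.3 at ρ = 0.5. From 70%, it is 4.0 and 11.8.

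**4. Simulation for 3a.** 350 participants in 8 sites, 4,000 trials per setting, outcome bounded at 0–168 days and baseline at 1–30 days.

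| Realised Spearman correlation | Rank-sum | Rank ANCOVA on baseline | Gain (points) |
|---|---|---|---|
| 0.19 | 79.2% | 80.9% | 1.7 |
| 0.28 | 80.6% | 83.6% | 3.0 |
| 0.37 | 79.9% | 85.3% | 5.4 |
| 0.47 | 81.2% | 89.5% | 8.3 |

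In a separate null simulation, type I error was 4.8% for both tests.

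**5. Simulation for 2d.** Week-24 prevalence 50% versus 35% and baseline prevalence 60%, all assumed.

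| Realised phi | Chi-squared | Logistic with baseline | Gain (points) |
|---|---|---|---|
| 0.20 | 80.8% | 82.9% | 2.1 |
| 0.30 | 80.8% | 84.8% | 4.0 |
| 0.39 | 80.3% | 87.2% | 6.9 |
| 0.49 | 80.8% | 90.6% | 9.8 |

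**6. Abstinence (3b).** Entry requires moderate or severe opioid use disorder, so few participants should be abstinent for 30 days at baseline; 0–5% was assumed. With week-24 abstinence of 22% versus 35%, adjusting for baseline abstinence moved power from 74.1% to 74.0% (none abstinent at baseline). It moved from 74.2% to 74.5% with 5% abstinent and a prognostic odds ratio of 3, and from 72.1% to 73.9% with an odds ratio of 6. That is 0 to 2 points. The gain from baseline days of use was not estimated.

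**7. Site.** For 3a with an assumed intraclass correlation of 0.05, adding site to the baseline-adjusted model moved power from 83.1% to 84.2% (ρ = 0.3) and from 89.3% to 90.1% (ρ = 0.5). With no site effect it made almost no difference. The contribution is about 0 to 1 point.

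**The case against.** The strongest reply is that the plan already provides adjusted analyses. Section 17.9.1 commits to GEE models for the secondary outcomes, its covariate list is open, and severity of opioid use disorder is related to baseline use. The entry for 3b allows covariates, and the wording for 3a does not rule out a stratified or adjusted rank method. All of this is correct. It does not settle the point, because the baseline measures and site are not named and the GEE results are not ranked above the listed tests.

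Other objections also stand:

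- **Different quantities in 3a.** The outcome covers 24 weeks. Baseline TLFB covers a shorter window of variable length. It is a related covariate and not the same measurement, which is one reason the correlation cannot be presumed high.
- **Change of target.** A logistic coefficient is a conditional odds ratio, whereas chi-squared compares marginal proportions. Standardizing to a risk difference deals with this. Rank ANCOVA gives no directly readable effect size.
- **Self-report.** Baseline adjustment corrects chance imbalance and does nothing about reporting bias in an open-label trial. The plan treats that separately, with urine confirmation for 3b and a urine-based confirmatory analysis for 3a.
- **Difference from the primary model.** Secondary tests need not mirror it. Leaving site out is a missed opportunity and not an error.
- **Validity.** The stated tests are valid, and no power target is set for them.

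**Conclusion.** The point stands as a free improvement. For 3a and 2d the stated tests leave aside baseline information already collected, and 17.9.1 neither names that information nor says which analysis leads. The gain is about 2 to 10 points of power. That rests on 80% power for the unadjusted test, two-sided alpha of 0.05 and correlations of 0.2 to 0.5, none of which the documents give. Site is worth including mainly because it stratified the randomization.

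A reader might go further in three ways that the documents do not support:

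- **That these outcomes are analysed only without adjustment.** Sections 17.9 (3b) and 17.9.1 show otherwise.
- **That the plan gives away at least 5 points.** This needs a correlation of about 0.35 or more when unadjusted power is 80%. At 0.2 to 0.3 the gain is about 2 to 4 points.
- **That abstinence gains as much.** Through its own baseline status it gains 0 to 2 points, because nearly everyone enrolled is expected to be using.

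These are secondary outcomes without Type I error control. The non-inferiority conclusion on viral suppression does not depend on them.

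**What to change.** In Section 17.9, name the adjusted analysis as the lead one for each outcome and fix its covariates in advance:

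- **3a:** rank ANCOVA, or the count model of 17.9.1, with baseline TLFB opioid days and site. Define the covariate as the 30 days before consent so that the window is the same for everyone. If rank ANCOVA is used, report a difference in days beside it.
- **2d:** for each week-24 RAB item, logistic regression on arm, the item's baseline value and site, reported as a standardized risk difference with its interval.
- **3b:** logistic regression on arm, baseline opioid days and site, also reported as a standardized risk difference. Claim no power gain.

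Keep the rank-sum and chi-squared tests as supporting analyses. State in 17.9.1 that any further covariate adjustment is supportive.

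The cost is SAP wording and a little programming for the standardization. No new data are needed, and sample size, visits and the primary analysis do not change.

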11.0 HIV-RELATED MEASURES

11.1 Antiretroviral Medication Prescription and Adherence

Since HIV viral suppression is most strongly influenced by optimal use of ART, evaluation of adherence to one's ART regimen is essential. Self-reported antiretroviral use and adherence will be assessed using a Medication Adherence questionnaire with visual analogue scale [142, 143] that is administered at baseline, treatment initiation, and weeks 4, 8, 12, 16, 20 and 24 weeks or the end of study visit (if not week 24) for assessment of secondary outcome if participant is prescribed ART at the time of follow-up visits. The Medication Adherence questionnaire asks the participant about adherence to HIV medications in the past month. We will assess the proportion of participants taking 100% of prescribed ART doses, based on visual analogue scale responses, in the past month at baseline, treatment initiation, and weeks 4, 8, 12, 16, 20, and 24 for those prescribed ART (proportion; self-reported medication adherence measure).

Because self-reported use of specific antiretrovirals has limited reliability when compared with medical record review [144, 145], we will confirm ART use with medical record review at baseline and 24 weeks (or the end of study visit, if not week 24) using the ARV Medication Log to assess the secondary outcome of ART prescription. Specifically, we will assess change in the proportion of participants prescribed ART within 24 weeks following randomization, compared to baseline (binary; medical record abstraction).

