17.0 STATISTICAL ANALYSIS

17.1 Primary Objective of the Analysis

The Primary objective of the CTN-0067 CHOICES scale-up study is to discover whether HIV clinic-based XR-NTX is non-inferior to TAU with respect to HIV viral suppression in HIV-infected participants with opioid use disorder. We have chosen a non-inferiority margin of 0.75. That is, we will reject the null hypothesis of inferiority of XR-NTX to TAU in favor of non-inferiority if the lower 95% confidence limit for the ratio $\frac{\text{Pr}(\text{suppressed}|\text{NTX})}{\text{Pr}(\text{suppressed}|\text{TAU})}$ is strictly greater than 0.75. We anticipate a sample size of 350 (175/arm) will grant at least 80% power for the non-inferiority conclusion.

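### The mediation model specifies no baseline adjustment, so if treatment shifts opioid use appreciably, shared baseline severity can produce a significant opioid-use-to-adherence pathway where none exists

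*Combined protocol and SAP*

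**What the plan says.** Section 17.9, under Mediation Analysis, defines path a as the effect of the intervention on the mediator (substance use) and path b as "the effect of the mediator on the outcome or next proximal intermediate outcome" (HIV medication adherence). The decision rests on the product: "There is significant mediation if the product of these two paths" exceeds zero, and "Statistical significance will be assessed using bias-corrected bootstrap confidence intervals on the product terms". The power statement is that "we should have over 80% power for mediation when the standardized path coefficients (a and b) are .164". The plan then translates a coefficient of that size into variance explained, "which corresponds to approximately 2.7% shared variance between the outcome and predictor variable". The paragraph names no covariate, no baseline value of mediator or outcome, and no sensitivity analysis for confounding. For the full mediational path it points to a section 1.2.1; in this document the conceptual model is Figure 2, section 4.1.1.

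Baseline measures exist. Section 14.3 states: "Baseline TLFB assesses use in the 30 days prior to informed consent through to the date of the baseline visit". ASI-Lite drug use is also taken at baseline (14.2). Section 11.1 describes an ART adherence questionnaire "that is administered at baseline, treatment initiation, and weeks 4, 8, 12, 16, 20 and 24 weeks", but the adherence measure applies only to those prescribed ART. Covariate adjustment, including severity of opioid use disorder, appears in 17.9.1 for separate GEE models of the secondary outcomes.

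**The concern.** Treatment is randomized, so path a is an unconfounded comparison. Opioid use during follow-up is not randomized, so path b is an observational association inside the trial. Section 4.1 itself cites evidence that opioid use disorder goes with lower ART adherence. A participant with heavy use at entry may report more use days over 24 weeks and also adhere less, for reasons unrelated to the use during follow-up. An unadjusted path b then picks up baseline severity.

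Adherence as mediated by opioid use days is a stated secondary aim (2.1, 5.2, 6.1), and Type I error is not controlled for secondary analyses (17.9.1). A positive finding would be read as support for the causal chain in section 4.1, when it could reflect case mix.

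**Working it through.** **Inputs from the documents.** N = 350, 1:1 ("We anticipate a sample size of 350 (175/arm) will grant at least 80% power for the non-inferiority conclusion"); standardized a = b = .164; bias-corrected bootstrap interval on a*b (17.9). The interval level is not stated; 95% two-sided is assumed.

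**Inputs assumed.** A baseline severity U with loading rm on follow-up opioid use and ry on adherence (in absolute value): 0.3/0.2, 0.4/0.3, 0.5/0.4. The documents give the direction of the association but no size. Mediator and outcome are treated as continuous.

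**Step 1: reproduce the plan's figure.** .164² = .0269, which agrees with 2.7%. Simulating treatment → use → adherence with a = b = .164 and no confounding (2,000 trials, 1,000 bootstrap draws each) gives 81.7% power, in agreement with the plan's claim. The percentile bootstrap gives 75.2% and joint significance 76.6%, so the claim depends on the bias-corrected method the plan names.

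**Step 2: size of the spurious path b.** Set true b = 0. Given treatment, cov(use, adherence) = rm·ry and var(use) = 1 − a². The unadjusted coefficient is therefore b* = rm·ry/(1 − a²). At a = .164:
- 0.3/0.2: .06/.9731 = .062
- 0.4/0.3: .12/.9731 = .123
- 0.5/0.4: .20/.9731 = .206

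The simulated means were .065, .124 and .207.

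**Step 3: closed-form check, middle case.** The partial correlation of use and adherence given treatment is .12/√.9731 = .1216. Then z = .1216·√350/√(1 − .1216²) = 2.29, so path b is significant with probability Φ(2.29 − 1.96) = .63 (simulated: .628). Path a has z = .164·√350/√(1 − .164²) = 3.11, probability .875. Both are significant in .63 × .875 = 55% of trials, against 54-56% in joint-test simulations.

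**Step 4: the planned test.** Bias-corrected bootstrap on a*b, true b = 0, N = 350, 600 trials per cell (Monte Carlo error up to about 2 points):

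| Loadings | a = 0, unadjusted | a = .164, unadjusted | a = .164, U fully adjusted | a = .164, adjusted by a proxy of reliability 0.7 |
|---|---|---|---|---|
| none | 0.2% | 7% | – | – |
| 0.3/0.2 | 2% | 28% | not run | not run |
| 0.4/0.3 | 4% | 63% | 10% | 16% |
| 0.5/0.4 | 6% | 86% | 7% | 30% |

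The proxy column follows from the bias left over: 0.3·rm·ry/(1 − a² − 0.7·rm²). This is .036/.861 = .042 and .060/.798 = .075; the simulated means were .042 and .073.

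**Step 5: dependence on a.** Joint test, loadings 0.4/0.3, N = 350: about 3% at a = 0, 9-11% at .05, 28-31% at .10 and 54-56% at .164.

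**The case against.** Several points on the other side have force.

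- **Severity alone does not suffice.** A reader might infer that baseline severity by itself makes the pathway significant. Significance is judged on a*b and path a is randomized. With a = 0 the product test stays at 2-6% over the range shown. This stands.
- **Nor does any treatment effect, however small.** Step 5 shows about 10% at a = .05. The value .164 is the plan's power threshold, not a predicted effect. The design alternative for suppression is no difference between arms (17.12), so a small a is plausible. This stands; the problem grows with a.
- **Sign.** Read literally, 17.9 counts only a product above zero. With a negative confounded b, that needs XR-NTX to lower use more than TAU. In the pilot the fall was 19 to 10 days on TAU (n = 12) and 18 to 13 on XR-NTX (n = 10) (4.3). If that direction held, the literal rule would almost never declare mediation. The rates above count an interval excluding zero on either side, the usual reading of a bootstrap interval.
- **The plan may intend covariates.** Section 4.1 says the conceptual model includes further covariates, and its figure is not available here. So the fair statement is that no adjustment is specified, not that adjustment is ruled out. But that sentence names no covariate and describes the conceptual model; an analyst could not derive an adjustment set from it.
- **The strengths are assumed.** Entry criteria (moderate or severe disorder, HIV RNA above 200) may narrow the range of severity and weaken the correlations. The protocol's adherence outcome is also binary among those prescribed ART, whereas the simulation is continuous. The rates illustrate the mechanism and do not forecast this trial.

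**Conclusion.** The point holds in a conditional form. As written, the structural model leaves its one non-randomized path unadjusted. If treatment moves opioid use by about the amount the plan powers for, false mediation would be declared in roughly 28% to 86% of trials under loadings from 0.3/−0.2 to 0.5/−0.4, against about 7% with no confounding. If treatment does not move opioid use, there is no material inflation.

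A reader might also infer that adjustment cures the problem. The 7-10% rate assumes the confounder is measured without error. Timeline Follow Back and ART adherence are self-reported, and at reliability 0.7 the rate is 16-30%: much better than 63-86%, but not nominal. Adjustment therefore needs a sensitivity analysis alongside it.

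The figures rest on assumed loadings, a 95% two-sided interval, continuous variables and N = 350. This affects one secondary aim and does not touch the primary non-inferiority conclusion. It should be changed because the better analysis uses data the trial already collects.

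**What to change.** In 17.9, name the covariates of the structural model and enter them in both the mediator and the outcome equation:
- baseline Timeline Follow Back opioid days;
- baseline ART status as an on-ART indicator, with baseline adherence entered as its interaction with that indicator, so that participants off ART at entry are retained;
- baseline alcohol use disorder and site, both already in the primary model (17.2).

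Make this the reported mediation analysis. Add a sensitivity analysis showing how strong unmeasured or error-prone confounding of path b would have to be to remove the result, and describe any finding as conditional on no residual confounding. State the interval level and whether a product of either sign counts. Correct the cross-reference to section 1.2.1. Reconcile 11.1 with 12.7, which describes the Medication Adherence form as tracking addiction pharmacotherapy, so that the source of baseline ART adherence is clear.

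Cost: SAP wording, a few model terms and a more cautious conclusion for one secondary aim. No visits, participants or measurements are added.
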